Estimations will be performed using the same multiple imputation approach as described previously. In each treatment arm, a penalty δ will be added to the imputed values ($\delta = 0$ corresponds to the MAR assumption) in the HbA1c multiple imputation step.

The documented hypoglycemia status will be imputed as described previously following the HbA1c imputation with various δ .

To investigate how the conclusions for the composite endpoint depend on the adopted values δ , the testing will be repeated over a range of plausible values for the pairs (δ_{Toujeo} , $\delta_{\text{std_care_basal_insulin}}$). The δ values range from -1 to 1 by 0.1, in each treatment group. Results will then be summarized using graphs.

The smallest value of δ_{Toujeo} for a value of $\delta_{\text{std_care_basal_insulin}}$ equal to 0 which will statistically reverse the conclusion for the composite primary endpoint will be assessed and interpreted from its clinical plausibility.

- **Sensitivity analysis excluding patient data from sites at which research activities were terminated due to non-compliance.**

A sensitivity analysis using the same method as for the primary efficacy analysis will be performed excluding patient data from sites at which research activities were terminated due to ongoing non-compliance with the clinical protocol and violations of GCP.

Sites [REDACTED] and site [REDACTED] are the two concerned. They will be excluded for a sensitivity analysis at 6 months.

Subgroup Identification based on Differential Effect Search

If superiority of Toujeo with respect to standard-of-care basal insulin is not shown in the primary efficacy analysis, an exploratory analysis will be conducted to identify potential subgroups of patients with enhanced treatment effect of Toujeo versus standard of care (Lantus or Levemir) basal insulin.

A procedure based on Subgroup Identification based on Differential Effect Search (6) will be employed to identify such subgroups of potential responders.

The outcome variable used in the SIDES method is the primary endpoint of the study which is the proportion of patients with individualized HbA1c target at 6 months, without any documented symptomatic or severe hypoglycemia.

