Patient characteristics on which potential subgroups will be defined, include randomization strata which are used in the primary efficacy analysis and other variables collected at baseline: randomization strata; SU use (y/n), GLP-1 RA use (y/n), baseline HbA1c (as continuous), baseline age, race/ethnicity, gender, baseline fasting glucose level, baseline BMI, duration of diabetes, diabetic disease history (diabetic retinopathy, diabetic sensory or motor

neuropathy, diabetic autonomic neuropathy, diabetic nephropathy), comorbidity (coronary artery bypass graft, percutaneous coronary intervention, ischemic vascular disease, thoracic aortic aneurysm, chronic heart failure, prior myocardial infarction, chronic renal failure or end stage of renal disease, dementia, blindness, and leg amputation). Since HbA1 target as per HEDIS depends on age and comorbidity, both already included, it will not be added to the list of covariates for subgroup search.

The global procedure includes the following steps:

- Balanced allocation procedure:

The data is split into one training data set on which the subgroup identification procedure will be applied, and one or several validation data set. This allocation procedure is based on an imbalanced score so that the distribution of patients' treatment and covariates is balanced between sets.

- SIDES recursive partitioning algorithm:

Subgroups are constructed from the training data set by recursively partitioning from covariates the data set into two subgroups at each parent group so that the treatment effect in one group is maximized compared to the other.

- Validation of identified candidates subgroups:

One validation set is used to confirm or reject candidate subgroups identified in the previous step based on-treatment effect p-value estimated on the validation set.

Note:

As specified in the article (6), the identification of candidate subgroups step can be applied to the entire data set, and confirmation performed in a subsequent independent study.

This will be the preferred option: the dataset will not be divided in training and test datasets, and only Step 2 (SIDES recursive partitioning algorithm) will be applied.

The SIDES recursive partitioning algorithm can be described as follows:

Consider the current parent subgroup. At the beginning, no covariate is used to define subgroup and the parent subgroup is the entire training set.

- Among covariates not already used to define parent subgroup,

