- For each covariate, consider all possible splits of the covariate into two child subgroups (the number of possible splits depends on the type of the covariate),
- If the subgroup with the larger treatment effect of one split has a sample size lower than a pre-defined threshold, then the split is excluded,
- For each split among all splits of the previous step, calculate the splitting criterion that aims at maximizing the differential effect between the two child subgroups,

- $$\rho = 2 \left[1 - \phi \left(\frac{Z_1 - Z_2}{\sqrt{2}} \right) \right],$$

- Where Z_1 and Z_2 denote the Z-statistics for efficacy of the subgroups pair composing one split, and ϕ represents the standard normal distribution function,
- Apply multiplicity adjustment to splitting criterion, based on modified Sidak correction, for covariates with more than two levels.
- Order all splits in terms of adjusted splitting criterion, and select the best M splits, where M is a pre-defined value.
- From each pair composing one split, select the subgroup with the larger treatment effect. These subgroups are called “promising child subgroups”.
- If a promising child subgroup meets the continuation criterion, that is if $\rho_c \leq \rho_p$ where ρ_c , respectively ρ_p , are the p-values of treatment effect for child, respectively parent, subgroups; then it is added to the set of parent groups.
- In addition of meeting the continuation criterion, if a promising child subgroup meets the selection criterion, it is added to the set of candidate subgroups return at the end of the recursive search algorithm. Treatment effect p-values of promising child subgroups are adjusted using a standard resampling-based method to have a weak control of type I error at a level α . Then, the selection criterion is met if the adjusted p-value in the subgroup is significant at a pre-defined level α .
- Call recursively the algorithm on each updated parent subgroups. The algorithm stops when a maximum number of L covariates are used to define parents, where L is pre-defined, or when no promising child subgroup meets the continuation criterion.

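### The SIDES splitting criterion is printed with a signed difference and no labelling rule, so the ranking of candidate splits can depend on how a covariate is coded

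*SAP*

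**What the plan says.** The search is conditional and exploratory: "If superiority of Toujeo with respect to standard-of-care basal insulin is not shown in the primary efficacy analysis, an exploratory analysis will be conducted" (SAP 2.4.4.1). The search uses the whole data set, since "the dataset will not be divided in training and test datasets, and only Step 2 (SIDES recursive partitioning algorithm) will be applied".

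The steps that matter here, in the order given in SAP 2.4.4.1, are:

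1. A split is dropped if its better-responding child is too small.
2. For each remaining split, "calculate the splitting criterion that aims at maximizing the differential effect between the two child subgroups". The printed formula is rho = 2[1 - Phi((Z1 - Z2)/sqrt(2))], where Z1 and Z2 "denote the Z-statistics for efficacy of the subgroups pair composing one split".
3. "Apply multiplicity adjustment to splitting criterion, based on modified Sidak correction, for covariates with more than two levels".
4. "Order all splits in terms of adjusted splitting criterion, and select the best M splits, where M is a pre-defined value". No value of M is given.
5. "From each pair composing one split, select the subgroup with the larger treatment effect".
6. The children kept must then pass a continuation criterion and a selection criterion based on resampling-adjusted p-values.

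**The concern.** The stated aim has no direction: a split is good if the treatment effect differs between its two children, whichever child does better. The factor 2 also marks rho as a two-sided quantity. Both require a criterion that is unchanged when the two children swap labels. The printed formula changes, because it takes Z1 - Z2 with its sign.

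The text does not supply the missing convention. Steps 1 and 5 above both refer to the child with the larger effect, but neither says that this child is number 1. If Z1 were always the better child, step 5 would repeat a choice already made.

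At stake is the planned search for responders after a missed primary endpoint. A literal implementation could discard the most informative splits at the ranking step because a variable was coded no/yes instead of yes/no. Later steps cannot recover them, because the continuation and selection criteria act only on children of the best M splits. SAP section 1.5 also prefers SIDES partly because it corrects for multiplicity, and an adjustment fed values above 1 fits poorly with that reason.

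**Working it through.** The SAP gives no numerical SIDES result, so there is no figure to reproduce. The check evaluates the printed formula.

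**Inputs.** The formula and the definition of Z1 and Z2 come from SAP 2.4.4.1. The Z pairs are chosen for illustration.

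**Step 1: effect of swapping labels.** Write x = (Z1 - Z2)/sqrt(2). Since Phi(-x) = 1 - Phi(x),

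rho(Z1, Z2) + rho(Z2, Z1) = 2[1 - Phi(x)] + 2 Phi(x) = 2.

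So if one labelling gives a small value p, the other gives 2 - p. Any split with Z1 < Z2 scores above 1, and the larger the differential effect, the closer the score comes to 2. Because rho falls as Z1 - Z2 rises, small values rank best.

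**Step 2: numbers.** For Z = (3, 0), x = 3/1.414 = 2.121 and rho = 2[1 - Phi(2.121)] = 0.034. For Z = (0, 3), rho = 2[1 - Phi(-2.121)] = 1.966.

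| Z-statistics of the two children | rho, better child labelled 1 | rho, better child labelled 2 | rho with absolute difference |
|---|---|---|---|
| 3 and 0 | 0.034 | 1.966 | 0.034 |
| 2.5 and 0 | 0.0771 | 1.9229 | 0.0771 |
| 2 and 1 | 0.4795 | 1.5205 | 0.4795 |
| 3 and -1 | 0.0047 | 1.9953 | 0.0047 |
| 1 and 1 | 1.0 | 1.0 | 1.0 |

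The pair 3 and -1 shows the strongest contrast. Labelled the wrong way, it scores 1.9953 and ranks behind a split with no differential effect at all (1.0).

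**Step 3: which covariates are exposed.** Counting each listed complication and comorbidity as a separate yes/no variable gives SU use and GLP-1 RA use (2), gender (1), diabetic complications (4) and comorbidities (10): 2 + 1 + 4 + 10 = 17 binary covariates. The Sidak step is confined to covariates with more than two levels, so for these 17 the raw rho sets the rank.

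**Step 4: covariates with more than two levels.** These are race/ethnicity and the continuous variables. A Sidak-type correction works on powers of 1 - rho, which is negative once rho exceeds 1. The SAP does not print its modified form, so no adjusted values can be given for this plan.

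**Step 5: illustration of the ranking step only.** A simulation was run under assumptions that are not the SAP's: 300 trials for each M, 3324 patients, 20 independent binary covariates, response rates of 35.5% and 33%, and random relabelling of the two levels. With the signed formula, relabelling changed the set of best M splits in 66% of trials for M = 1, 94% for M = 3 and 100% for M = 5. With the absolute difference it never changed. These percentages describe the shortlist of splits, not the subgroups finally reported.

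**The case against.** Four points can be made for the plan.

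- **The bars may be a conversion loss.** The point rests on thin vertical strokes in one typeset formula. Nearby notation is loose: the normal distribution function appears as a lower-case phi, and one letter serves both for the criterion and for the treatment-effect p-values. This stands as a reason to look at the original page before changing anything.
- **The direction is implied.** The better child is already identified in the size check before the formula, and taking it as Z1 is the sensible reading. A program that puts that child first, or scores both orders, would behave correctly. This stands as a description of likely intent, but no sentence makes it the rule.
- **The cited SIDES article and the program may settle it.** They may, but neither is part of the plan, and the SAP prints its own formula.
- **The consequence is small.** The search is exploratory and conditional, and a value near 2 would probably be noticed when the program is first run. This stands and limits the importance of the point.

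A reader might also infer more than the documents support. One such inference is that a given recode must change the subgroups reported. That depends on M and on the later criteria; if M covered every split, the ranking would not matter. Another is that about half of all splits must score above 1, which follows only if labels are arbitrary. A third is that affected splits cannot be ranked at all; they are ranked, but badly. Nor can specific Sidak-adjusted values be attributed to the plan.

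**Conclusion.** The point holds for the formula as printed. It is asymmetric in the two children, conflicts with its own direction-free aim, and can place the strongest differential effects last (1.966 instead of 0.034 for Z-statistics 0 and 3). For the 17 binary covariates the order of splits can depend on coding. For the others, a value above 1 is not a valid input to the planned adjustment.

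This assumes that the bars are absent from the original page and that the program follows the text without its own labelling convention. Any effect on the reported subgroups cannot be quantified from the documents. It is a minor correction, confined to an exploratory analysis run only if primary superiority is not shown, with no bearing on the primary test, its alpha or the sample size.

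**What to change.** First check the formula on the original SAP page. If the bars are absent there, either print rho = 2[1 - Phi(|Z1 - Z2|/sqrt(2))] or add a sentence defining Z1 as the larger of the two Z-statistics, in both cases before the Sidak step. Then confirm that the SIDES program uses the same rule, for example by exchanging the levels of one binary covariate and checking that the ranking does not move. The cost is one symbol or one sentence in the SAP and a short program check. No data collection or other analysis changes.

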2.4.4.2 Analyses of secondary efficacy endpoints

Change in HbA1c

The change in HbA1c from baseline to 6 months will be analyzed using an analysis covariance (ANCOVA) model. The model will include a fixed categorical effect of treatment arm, HbA1c target and other randomization strata; SU use (y/n), GLP-1 RA use (y/n), as well as baseline BMI (as continuous) and baseline HbA1c (as continuous).

The change in HbA1c from baseline to 12 months will be analyzed a MMRM approach under the MAR framework, using an adequate contrast at Month 12. The model will include fixed categorical effects of treatment arm, visit, treatment-by-visit interaction, HbA1c target and other randomization strata; SU use (y/n), GLP-1 RA use (y/n), and baseline A1c (as continuous), as well as baseline HbA1c-by-visit interaction. Both 6 months and 12 months HbA1c data will be included in the MMRM model.

The analysis of HbA1c is based on patients in the ITT population. For those with missing HbA1c value at 6 months, the change in HbA1c will be missing. Therefore, those patients will not be included in the analysis.

As sensitivity analysis, the imputed HbA1c values at 6 months and 12 months described in [Section 2.4.4.1](#) will be used to repeat the change in HbA1c from baseline to 6 months and to

12 months analysis models. The estimates from the 100 fitted models will be combined to provide an overall estimate with corresponding CIs for the treatment differences in change from baseline in HbA1c to 6 months and 12 months.

Change in FPG and body weight

The change in FPG and body weight from baseline to 6 and 12 months will be analyzed in a similar fashion to the change in HbA1c.

Other binary endpoints

The proportion of patients with HbA1c <8% and <7% without documented symptomatic (BG \leq 70 mg/dL) or severe hypoglycemia at 6 months and of patients with HbA1c <8% and <7% at 6 months will also be analyzed by the same logistic regression model as for the primary efficacy analysis.

The proportion of patients with individualized HbA1c target attainment without documented symptomatic (BG \leq 70 mg/dL) or severe hypoglycemia at 12 months, and the proportion of patients with individualized HbA1c target attainment without documented symptomatic (BG <54 mg/dL) or severe hypoglycemia at 6 and 12 months be analyzed as described for the primary endpoint.

Health resource utilization

Detailed analysis methods for health resource utilization will be described in a separate analysis plan.

Subgroup factors

For subpopulations of sufficient size, additional subgroup analyses may also be performed.

The following treatment effects across different subgroups (baseline or screening factors), where appropriate according to subgroup size, will be explored on primary efficacy endpoint:

- Gender (male, female),
- Randomization strata of individualized HbA1c target (<8%/<7%),
- Randomization strata of GLP-1 RA use (y/n),
- Randomization strata of SU use (y/n),
- Baseline HbA1c category (<9%/≥9%),
- Age group (<65, [65–75] and ≥75 years of age),
- Baseline BMI categories (<25, [25-30], [30-40] and ≥40 kg/m²),
- Category of duration of diabetes (<10, ≥10 years).

For each subgroup, the primary efficacy variable will be analyzed in the ITT population using post-baseline HbA1c data available on the 6-month randomized treatment period. A similar logistic regression as described for primary analysis will be applied adding the corresponding subgroup factor, subgroup factor-by-treatment interaction and subgroup factor-by-visit-by-treatment interaction (for 12-month analysis only).

When the subgroup considered is equal to one of randomization stratum or is part of one of the adjustment factor, this randomization stratum/adjustment factor is removed from the model.

The significance level of the treatment-by-subgroup factor interaction term at Month 6 will also be determined for each factor for descriptive purpose. Forest plots will be provided.

The individual components of the composite endpoint of the primary efficacy variable will also be assessed for each subgroup factor.

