2.1.3.2 Secondary efficacy endpoint(s)

- Change in HbA1c from baseline (obtained at screening visit within one week of study initiation) to 6 months,
- Proportion of patients who remain on assigned basal insulin therapy (persistent with assigned therapy) at 6 and 12 months,
- Proportion of patients with individualized HbA1c target attainment per HEDIS criteria at 6 months without documented symptomatic ($BG < 54$ mg/dL) or severe hypoglycemia at any time of day from baseline to 6 months,
- Proportion of patients with individualized HbA1c target attainment per HEDIS criteria at 12 months without documented symptomatic ($BG < 54$ mg/dL) or severe hypoglycemia at any time of day from baseline to 12 months, and,
- Proportion of patients with individualized HbA1c target attainment (per HEDIS criteria) at 12 months without documented symptomatic ($BG \leq 70$ mg/dL) or severe hypoglycemia at any time of day from baseline to 12 months.

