2.4.4.1 Analysis of primary efficacy endpoint

The primary efficacy analysis will be performed on the ITT population, using all post-baseline HbA1c data available and hypoglycemia events collected on the 6-month randomized period, regardless of IMP discontinuation.

The primary efficacy endpoint: proportion of patients reaching individualized HbA1c target at 6 months without documented symptomatic ($BG \leq 70$ mg/dL) hypoglycemia will be analyzed using a logistic regression model, adjusting for HbA1c target and other stratification factors used at randomization: SU use (y/n), GLP-1 RA use (y/n) and baseline HbA1c (as continuous). a superiority test will be performed to compare this proportion between treatment groups at IA

(2-sided, alpha = 0.010) and at final 6-month analysis (2-sided, alpha = 0.046). Treatment difference will be assessed by odds ratios and CIs. For the primary efficacy analysis, the randomization strata from IVRS will be used.

Patients with missing HbA1c data at 6 months will be regarded as not having reached HbA1c target. In order to examine the consistency of this analysis, the individual components of HbA1c target attainment and absence of any documented symptomatic (BG ≤70 mg/dL) or severe hypoglycemia will also be evaluated. Each individual component (HbA1c target attainment at 6 month, or absence of any documented symptomatic [BG ≤70 mg/dL] or severe hypoglycemia), will be compared between treatment groups, respectively, using same logistic regression model as the primary efficacy analysis.

Sensitivity analyses

The sensitivity analyses of primary efficacy endpoint will be performed at time of 6-month database lock.

- **On-treatment sensitivity analysis.**

A sensitivity analysis for the primary efficacy endpoint will be performed on the 6-month on-treatment period, as defined in [Section 2.1.3](#).

- **Multivariate analysis.**

As a sensitivity analysis, a multivariate analysis will be performed, adding the following baseline covariates in the model: BMI, duration of diabetes, baseline PAM score, hypoglycemic history and age. a backward selection procedure at 0.10 level will be used get the final model with these exploratory factors. Treatment effect will be re-evaluated based on the final model.

Country (USA/Canada) and US region effect systematic group difference will be explored.

- **Sensitivity analysis of primary efficacy endpoint with randomization strata from e-CRF.**

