2.5.2 Data handling conventions for secondary efficacy variables

Fasting condition

FPG measurement not collecting in fasting condition will not be used in the analyses.

Invalid laboratory data

HbA1c or FPG measurements flagged as invalid by the laboratory will not be used in the analyses.

Treatment persistence/switch

A switch is defined by:

- A switch from Toujeo IMP to any commercial “standard of care” basal insulin or,
- A switch from “Lantus or Levemir” IMP basal insulin to commercial Toujeo.

Change in “standard of care” basal insulin to another basal insulin not being considered as a “switch”.

Remain on assigned therapy is defined by,

- Neither permanently withdraw,
- Nor switch:
 - From IMP Toujeo to Lantus or Levemir insulin,
 - Or from “standard of care” basal insulin to commercial Toujeo,
- Assigned therapy refers to the treatment allocated by IRT: Toujeo or Lantus/Levemir,
- Commercial Toujeo not being allowed in both treatment arms.

Persistence is defined by,

- Remained on assigned therapy.

HbA1c target and severe and or symptomatic hypoglycemia

HbA1c target missing data handling,

- Patients with missing HbA1c data at respectively Month 6 and Month 12 will be regarded as not having reached the HbA1c target (ie, as failure) at each given time-point.

Symptomatic hypoglycemia target missing data handling

In case of at least one symptomatic event with glycemic value missing it will be considered that the patients experiences at least:

- One document symptomatic hypoglycemia (BG ≤ 70 mg/dL [≤ 3.9 mmol/L]) and,
- One document symptomatic hypoglycemia (BG < 54 mg/dL [< 3.0 mmol/L]).

In case of at least one symptomatic event with timing missing it will be considered that the patients experiences at least:

- One symptomatic hypoglycemia event occurring at any time of the day and,
- One nocturnal symptomatic hypoglycemia event.

Composite endpoints missing data handling

- For each cases presented above regarding missing HbA1c values the patient will be considered as failure for each composite endpoint of the corresponding randomized period.
- For each case presented above regarding missing hypoglycemia event information the patient will be regarded as failure for each related composite endpoint.
- In case of premature end of study during the 6 month randomized period the patient will be considered as failure for each composite endpoint relative to the 6-month and the 12 month period.

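### The 12-month subgroup model for the composite endpoint contradicts its own data period and, if both visits are stacked and the listed terms fitted, gives invalid interaction tests

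*SAP*

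**What the plan says.** Under the Subgroup factors heading of SAP section 2.4.4.2, the primary efficacy variable is analysed in the ITT population "using post-baseline HbA1c data available on the 6-month randomized treatment period". The model is given as follows: "A similar logistic regression as described for primary analysis will be applied adding the corresponding subgroup factor", together with "subgroup factor-by-treatment interaction and subgroup factor-by-visit-by-treatment interaction (for 12-month analysis only". The one interaction p-value promised is this: "The significance level of the treatment-by-subgroup factor interaction term at Month 6 will also be determined for each factor for descriptive purpose". Eight subgroup factors are listed, and forest plots are planned.

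The model carried over is in SAP section 2.4.4.1, where the primary endpoint "will be analyzed using a logistic regression model, adjusting for HbA1c target and other stratification factors used at randomization". It has one outcome per patient and no patient effect, covariance structure or robust variance.

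For the continuous HbA1c endpoint the plan does name a repeated-measures method: "Both 6 months and 12 months HbA1c data will be included in the MMRM model". It names none for the binary composite.

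**The concern.** Months 6 and 12 are the only scheduled post-baseline HbA1c visits, so a visit interaction has meaning only if each patient contributes two outcomes. Those outcomes are positively related by construction. The 12-month composite counts hypoglycemia over a window that contains the first six months ("severe hypoglycemia at any time of day from baseline to 12 months"), so an early event fails both composites. SAP section 2.5.2 adds a second link: "In case of premature end of study during the 6 month randomized period the patient will be considered as failure for each composite endpoint", and this applies to the 6-month and the 12-month period alike.

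An ordinary logistic fit ignores that link. The term list causes a further problem. With no visit, visit-by-treatment or visit-by-subgroup term, any general change in success between Month 6 and Month 12 has nowhere to go except the three-way term, and from there it distorts the treatment-by-subgroup term.

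At stake are the interaction p-values and subgroup estimates reported at the 12-month lock, across eight factors with no multiplicity adjustment.

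**Working it through.** The plan states no standard error, correlation or power for this model, so there is no figure of its own to reproduce.

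**Inputs from the documents.** 3324 patients, 1662 per arm (SAP 1.3.2), and the term list in SAP 2.4.4.2. The design rates are 33% for comparator and 33 + 5.5 = 38.5% for Toujeo. Their midpoint is 35.75%, taken as 36% success at Month 6.

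**Assumptions, not in the documents.** Success of 32% at Month 12, within-patient correlation r of about 0.5 (0.53 used below), a 50/50 subgroup, and no true treatment effect or interaction.

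**Step 1: listed terms, 0/1 coding.** Let T be treatment, S subgroup and V visit (0 = Month 6). The model holds T, S, T×S and T×S×V. Only the cell T = S = 1 has its own visit effect. The other three cells are forced to one level, the average of the visits (34%). With nothing truly present, the terms estimate:

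- T×S: logit(0.36) − logit(0.34) = −0.5754 + 0.6633 = 0.088
- T×S×V: logit(0.32) − logit(0.36) = −0.7538 + 0.5754 = −0.178

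Both should be zero. Each cell has 3324/4 = 831 patients. The variances on the logit scale are:

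- Month 6 cell: 1/(831 × 0.36 × 0.64) = 0.00522
- Month 12 cell: 1/(831 × 0.32 × 0.68) = 0.00553
- Visit-averaged cell, treated as independent rows: 1/(1662 × 0.34 × 0.66) = 0.00268

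T×S:

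- Naive SE = √(0.00522 + 3 × 0.00268) = 0.115.
- True SE = √(0.00522 + 3 × 0.00268 × 1.53) = 0.132.
- Rejection = P(Z > (1.96 × 0.115 − 0.088)/0.132) + P(Z < −(1.96 × 0.115 + 0.088)/0.132) = 14.9% + 0.9%, about 16%.

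T×S×V:

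- Naive SE = √(0.00522 + 0.00553) = 0.1037.
- True SE = √(0.00522 + 0.00553 − 2 × 0.53 × √(0.00522 × 0.00553)) = 0.0711.
- Rejection = P(Z > (1.96 × 0.1037 − 0.178)/0.0711) = P(Z > 0.35), about 36%.

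Simulations of the listed terms agree. T×S rejected in 14.5% of 600 trials in one and about 15% in another. T×S×V rejected in 26% and 55%. The three-way figure varies because it depends steeply on the assumed fall in success: the same formulas give about 16% if Month 12 success is 33% and about 61% if it is 31%. T×S moves from about 13% to about 20% over that range.

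**Step 2: listed terms, effect coding.** The three-way term is now orthogonal to the rest, and only the variance is wrong. Naive/true SE is 1/√(1+r) for T×S and 1/√(1−r) for T×S×V. Rejection rates are 2 × (1 − Φ(1.96/√(1+r))) and 2 × (1 − Φ(1.96/√(1−r))):

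| r | T×S | T×S×V |
|---|---|---|
| 0.3 | 8.6% | 1.9% |
| 0.5 | 11.0% | 0.6% |
| 0.7 | 13.3% | 0.03% |

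Simulations of this case gave 11% and 13.2% for T×S, and 0.7% and 0.5% for T×S×V.

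**Step 3: all lower-order terms added.** With visit reference-coded to Month 6, T×S uses one row per patient. Simulated rejection of the Month 6 interaction was 3.5% to 6.5% for r from 0.37 to 0.72 (400 trials per setting, simulation error about 1 point). That is essentially correct without any clustering. Patient-clustered variance brought the visit-averaged and three-way tests back to about 3% to 6%.

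**The case against.** The SAP never says that both outcomes are stacked, and its data sentence points the other way. Neighbouring text also suggests one model per time point. The overall 12-month composites are analysed as described for the primary endpoint. The parallel hypoglycemia subgroup analysis in SAP 2.4.5.1 handles the 6-month and 12-month periods separately, with no visit term. The visit term may simply be a stray. The only interaction p-value promised is the one at Month 6, which a full model estimates correctly. The work is descriptive, and the correlation and event rates above are not in the documents.

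Most of this stands, and it sets the limits of the point. Stacking is an inference, and a reader should not take it as a planned fit. It is nevertheless the only reading under which the written term can be estimated, and the contradiction with the data period is there whichever reading is right. The Month 6 defence needs lower-order terms that the SAP does not list. With the listed terms and 0/1 coding, the coefficient that would be read as the Month 6 interaction is biased (step 1).

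A reader might also infer that all subgroup standard errors will be too small. The documents and the arithmetic do not support that. The direction depends on the contrast and the coding: too small for visit-averaged effects, too large for the three-way term, and about right for a single-visit contrast in a full model.

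**Conclusion.** The paragraph is wrong as written, at low severity. It restricts the data to six months and at the same time requires a visit interaction. It takes that interaction into a one-row-per-patient logistic model without the lower-order visit terms or any handling of within-patient correlation.

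If both visits are stacked and the listed terms fitted, the treatment-by-subgroup test rejects in roughly 11% (effect coding) to 15% (0/1 coding) of trials at nominal 5%. The three-way test is either badly biased or rejects in under 1%. These sizes rest on an assumed correlation of about 0.5, success falling from about 36% to 32%, and an even subgroup split. The documents support a positive correlation but give no value for it.

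A reader might infer that effect modification on the 6-month primary endpoint is compromised. It is not. The visit term is confined to the 12-month analysis, the subgroup model at the 6-month lock has no visit term, and the primary test, sample size and interim boundary are unaffected.

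**What to change.** Preferred: delete the visit interaction and state that subgroup analyses use separate logistic models for the Month 6 composite and the Month 12 composite. Each model has one row per patient, the primary covariates, and the subgroup and treatment-by-subgroup terms. For the Month 12 model, change the data period to the 12-month randomized period.

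Alternative, if a change of effect between visits is of interest: fit a GEE logistic model with patient as cluster and robust variance. Include treatment, subgroup, visit, all three two-way interactions and the three-way term. State the visit coding and which contrast gives the Month 6 interaction.

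Either choice costs a short SAP rewording and a small programming change before the 12-month lock. No new data are needed.
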